### **5.3. Adjustments for Covariates**

N/A

### **5.4. Handling of Dropouts or Missing Data**

Any missing values at dialysis treatment level of an endpoint will not be imputed.

### **5.5. Interim Analyses**

No interim analysis is planned.

### **5.6. Multicenter Studies**

This is a multi-centers study. Due the similarity of hemodialysis treatments among the dialysis clinics, the center effect will not be considered in this study.

### **5.7. Multiple Comparisons/Multiplicity**

N/A

### **5.8. Use of an “Efficacy Subset” of Subjects**

N/A

### **5.9. Active-Control Studies Intended to Show Equivalence/Non-inferiority**

N/A

## 5.10. Examination of Subgroups

Due to small numbers of subjects in the study, subgroup analyses were not performed.

# 6. STATISTICAL ANALYSES

## 6.1. Disposition of Subjects

Frequencies will be for overall, by center, and for the treatment period.

The subject disposition table will include:

- The number of subjects who signed the informed consent.
- The number of subjects with screen failure.
- The number of subjects who were eligible.
- The number of subjects who were enrolled.
- The number of subjects who were discontinued in Optiflux, or in Endexo periods.
- The numbers of safety and analysis populations.
- The number of subjects and percent by category of major reasons for early discontinuation.

## 6.2. Protocol Deviations

Any protocol deviations will be listed. Summaries by category of protocol deviations may be presented if the number of protocol deviations is sufficiently large.

## 6.3. Analysis Populations

- **Safety Population (spop):** The spop (safety population) will include subjects who sign the ICF, are eligible, are enrolled in the study, and have at least one HD treatment with the dialyzer with Endexo.
- **Analysis population (apop):** The apop (analysis population) will include subjects who are in the spop, and have a minimum of 36 HD treatments with the dialyzer with Endexo.

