Statistical Methods	
Descriptive statistics (n, mean, standard deviation, median, minimum and maximum) will be presented for continuous endpoints. Frequency and percent will be presented for categorical endpoints. Any missing values of an endpoint will be treated as completely missing at random and will not be imputed.
 
Study analysis populations:
 
• Safety population (spop): Subjects who sign the ICF, are eligible, are enrolled in the study, and have at least one HD treatment with the dialyzer with Endexo.• Analysis population (apop): Subjects who are in the spop, and have a minimum of 36 HD treatments with the dialyzer with Endexo. 
Analysis for primary endpoint:
 
- For the K_{uf} for the dialyzer with Endexo, descriptive statistics will be presented. A 95% confidence interval will be calculated if appropriate. 
Analysis for secondary endpoints:
 
- For URR and spKt/V for the first study use of both dialyzers, descriptive statistics will be presented, and a 95% confidence interval will be calculated if appropriate.- For albumin and beta-2-microglobulin, the relative percent change $\{((\text{pre-HD} - \text{post-HD})/\text{pre-HD}) \times 100\}$ will be calculated. Descriptive statistics will be presented for the pre-HD and post-HD laboratory values and the relative percent change. The 95% confidence intervals will be calculated if appropriate.- Adverse events and device-related events per treatment will be calculated. The 95% confidence intervals will be derived if appropriate. 
Analysis for additional assessments:
 
- For the measurements of complement activation, the relative percent change $\{((30 \text{ minutes after the recorded start of HD} - \text{pre-HD})/\text{pre-HD}) \times 100\}$ will be calculated. Descriptive statistics will be presented for the "pre-HD" and "30 minutes after the recorded start of HD" laboratory values and the relative percent change. The 95% confidence intervals will be calculated if appropriate.- For thrombus formation:
• the number of subjects and percentages, and the number of HD treatments in each period for each grade category will be presented, and,
----------------------------	--

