## 2. STUDY DESIGN

### 2.1. General Description

This is a prospective, sequential, multi-center, open-label study with subjects on thrice-weekly (in-center) hemodialysis treatment.

Each subject will participate in a screening period, Optiflux period, Endexo period, and a follow-up visit.

- Screening Period

Screening, which will be up to 4 weeks in duration, begins with signing of the informed consent form (ICF). After the Screening Period is completed (with eligibility verified), the subject is enrolled and can proceed to the Optiflux Period.

- Optiflux period

The Optiflux Period is 12 HD treatments (visits 1 to 12) on the Optiflux dialyzer (4 weeks in duration). A maximum of two missed treatments are permitted within visits 2 to 11. The visit 12 cannot be missed during the Optiflux period.

- Endexo period

The Endexo period is 38 HD treatments on the dialyzer with Endexo (approximately 13 weeks in duration). The visit 13 cannot be missed. A maximum of four missed treatments are permitted within Visits 14-50.

- Follow-up visit

An in-center Follow-up visit is to be conducted within 1 week of the last scheduled study HD treatment.

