## **6.9. Analysis of Safety**

All safety measurements will be analyzed under safety population

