### **6.9.1 Adverse Events**

See Section 6.7.

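### The safety population carries a separate eligibility condition, so a subject treated with Endexo and later found ineligible may be left out of the safety tables

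*SAP*

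**What the plan says.** The protocol synopsis (Statistical Methods) defines the safety population as "Subjects who sign the ICF, are eligible, are enrolled in the study, and have at least one HD treatment with the dialyzer with Endexo". SAP 6.3 matches it: the population "will include subjects who sign the ICF, are eligible, are enrolled in the study" and have the same minimum exposure. The analysis population in SAP 6.3 is the subset of the safety population with 36 or more Endexo treatments, so it inherits the eligibility condition.

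On timing, SAP 2.1 states: "After the Screening Period is completed (with eligibility verified), the subject is enrolled and can proceed to the Optiflux Period". SAP 6.1 has a disposition line for "The number of subjects who were eligible", placed after screen failures and before the line for enrolled subjects.

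On use, SAP 6.9 states: "All safety measurements will be analyzed under safety population". For adverse events, however, 6.9.1 says only "See Section 6.7", and 6.7 puts every secondary endpoint under the analysis population. SAP 4.2 lists adverse events and device-related adverse events among the secondary endpoints. The measure planned in 6.7 is events per treatment.

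SAP 5.1 has all collected data listed, and 6.2 has all protocol deviations listed. Neither document says how to classify a subject whose ineligibility comes to light after treatment has begun.

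**The concern.** A safety population is normally defined by exposure. Here it also depends on eligibility, which can be judged again after exposure. Several criteria in the synopsis rest on dated windows or on history: laboratory values within 45 days, heparin prescription unchanged for 14 days, no antibiotics within 14 days, no hospitalization within 30 days, heart failure class, cirrhosis, known allergy to Endexo. An error in any of these could be noticed only after the subject had used the investigational dialyzer.

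Read literally, such a subject then belongs to neither population, and the events would not enter the summary tables. Summarizing adverse events with Endexo is the study's secondary objective, and in a study this small one subject is visible in the totals. The study is open-label, and no rule says who settles a late eligibility question or when, so the decision could be taken with that subject's events already known.

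**Working it through.** The documents give no figure for this point, so there is nothing to reproduce. The check has three parts.

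**1. Two readings of the eligibility condition**

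| Reading | Support | Effect on an enrolled, treated subject later found ineligible |
|---|---|---|
| Passed screening | SAP 2.1 verifies eligibility before enrollment; SAP 6.1 places it between screen failure and enrollment | Stays in; the condition removes no enrolled subject |
| True status | SAP 6.3 and the synopsis list it separately from enrollment and exposure | Leaves the safety population and the analysis population nested in it |

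Under the first reading the condition is redundant. Under the second it removes exposed subjects. Neither reading gives a reason to keep it in a safety population.

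**2. Size of one omitted subject**

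Inputs: 15 to 24 enrolled and 38 Endexo treatments per subject (synopsis). Share of enrolled subjects: 1/24 = 4.2%; 1/15 = 6.7%.

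For the effect on adverse event results, these are assumptions, not document figures: all N enrolled subjects are treated; one is omitted; each of the others has 38 treatments; the omitted subject has T treatments and an event rate k times that of the others. Results without the subject divided by results with the subject:

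- count ratio = 38(N−1) / [38(N−1) + kT]
- rate ratio = [38(N−1) + T] / [38(N−1) + kT]

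With T = 38, 38(N−1) is 38 × 14 = 532 for N = 15 and 38 × 23 = 874 for N = 24.

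| k | Count, N = 15 | Count, N = 24 | Rate, N = 15 | Rate, N = 24 |
|---|---|---|---|---|
| 0 | 1.000 | 1.000 | 570/532 = 1.071 | 912/874 = 1.043 |
| 0.5 | 532/551 = 0.966 | 874/893 = 0.979 | 570/551 = 1.034 | 912/893 = 1.021 |
| 1 | 532/570 = 0.933 | 874/912 = 0.958 | 1.000 | 1.000 |
| 3 | 532/646 = 0.824 | 874/988 = 0.885 | 570/646 = 0.882 | 912/988 = 0.923 |

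The count never rises. The rate falls only if k > 1, is unchanged at k = 1 and rises if k < 1. With T = 1 the pooled rate changes by less than 1% for k from 0 to 5. If the rate is instead averaged over subjects, as SAP 5.1 prescribes generally, the ratio is N/(N−1+k) whatever T is, which equals the T = 38 rate columns.

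**3. Which population adverse events use**

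SAP 6.9 points to the safety population. SAP 6.9.1 leads to 6.7, which points to the analysis population. The two cannot both hold. Under 6.7, anyone with fewer than 36 Endexo treatments is also left out. That includes a subject who misses the four treatments SAP 2.1 permits (38 − 4 = 34, below 36). Removing the eligibility condition alone would not bring these subjects into the 6.7 adverse event tables.

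**The case against.** The strongest reply is that the condition simply follows the screening sequence: consent, eligibility confirmed, enrollment, treatment. SAP 2.1 and the order of lines in 6.1 fit that reading, and nothing in either document says that subjects are removed retrospectively. This stands as a fair reading. It does not defend the wording, because on that reading the condition does no work and can be deleted without loss.

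A reader might infer that the Endexo adverse event results are understated, or biased downward. The documents do not support that. It would take an eligibility error, its discovery after exposure, the true-status reading and, for the rate, more events per treatment in that subject than in the others. None of these is shown to occur. Some criteria do screen out frailer subjects, but an out-of-window laboratory date or a missed antibiotic course need not mark one.

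A reader might also infer that the events would disappear. They would not: SAP 5.1 and 6.2 keep the data and the deviation in listings, and the synopsis requires adverse events to be captured from consent onward and serious ones reported to the sponsor within 24 hours. What could be lost is their place in the summary tables.

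Finally, only the synopsis of the protocol was available. Fuller protocol text might deal with late eligibility findings.

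**Conclusion.** The point holds as a conditional one. Both documents make eligibility a separate requirement of the safety population, and on the true-status reading a subject exposed to Endexo can be omitted from the safety summaries. Per subject, the stake is 4.2% to 6.7% of those enrolled and up to 38 Endexo treatments; the share of treated subjects would be somewhat larger if fewer are treated than enrolled. How many such subjects there might be is unknown, and may be none. The direction is settled for the event count, which cannot rise, but not for events per treatment. The conflict between SAP 6.9 and the route from 6.9.1 to 6.7 belongs to the same correction, because it decides whether a repaired safety population reaches the adverse event tables at all.

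**What to change.** 1. In SAP 6.3 and the protocol synopsis, delete the eligibility condition from the safety population. Define it as all enrolled subjects with at least one Endexo treatment, regardless of later eligibility findings.
2. In SAP 6.7 and 6.9.1, state that adverse events and device-related events are analysed in this safety population, which brings both sections into line with 6.9.
3. Do not move the eligibility condition into the analysis population while adverse events are still analysed there; that would exclude the same subjects again.

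The cost is a clause in each document and a sentence in the SAP, with no new data. The downside is that the safety tables may include a few events in subjects outside the intended population; a footnote can identify them.

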#### **4.2. Secondary Endpoint(s)**

The secondary endpoints include collecting the following data on the dialyzer with Endexo and the Optiflux dialyzer:

- The number of any adverse events and device-related adverse events.
- Urea Reduction Ratio (URR) and spKt/V (calculated from pre- and post-dialysis BUN) for the first study use of the dialyzers
- Pre- and post-HD serum albumin and  $\beta_2$ -microglobulin for the first use of dialyzers, visit 1 for Optiflux and visit 13 for dialyzer with Endexo.

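### Subjects lost during the Optiflux period belong to no analysis population, so their adverse events and treatments are left out of the Optiflux adverse event rate

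*SAP*

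**What the plan says.** **Populations.** SAP 6.3 limits the safety population (spop) to consented, eligible, enrolled subjects who "have at least one HD treatment with the dialyzer with Endexo". The analysis population (apop) takes those in the spop who also "have a minimum of 36 HD treatments with the dialyzer with Endexo". The Statistical Methods row of the protocol synopsis gives the same two definitions. No population is defined by exposure to Optiflux.

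**Order of treatment.** Under SAP 2.1 a subject is enrolled once screening is complete, then has 12 Optiflux treatments (visits 1 to 12), and only then starts Endexo at visit 13.

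**Endpoint.** SAP 4.2 and the synopsis name as a secondary endpoint, for both dialyzers, "The number of any adverse events and device-related adverse events". SAP 6.7 expresses it per treatment, and SAP 5.2 allows a 95% confidence interval for each period if adequate. The synopsis lists Optiflux among the investigational products and captures adverse events from signed consent.

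**Which population applies.** SAP 6.7 places all secondary endpoints, adverse events included, in the apop. SAP 6.9 says "All safety measurements will be analyzed under safety population", but its adverse event subsection, 6.9.1, only refers back to 6.7.

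**Early exits.** The disposition table in SAP 6.1 has a row for "The number of subjects who were discontinued in Optiflux, or in Endexo periods", together with the main reasons for early discontinuation. SAP 5.1 says that all collected data will be listed.

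**The concern.** The plan collects adverse events during the Optiflux period, foresees that some subjects will stop in it, and intends to report an event rate for that dialyzer. It has no population in which the events of those subjects can be summarised. Membership is decided by reaching visit 13, which is after the Optiflux exposure has ended. The Optiflux rate therefore describes only subjects who got through the Optiflux period.

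This matters because an early exit may be related to an adverse event. A serious event during a study treatment could then be counted in no adverse event table. It also matters because SAP 2.2 offers the Optiflux measurements as a within-subject control for comparisons as needed, so an error in the Optiflux rate carries into any contrast with Endexo.

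**Working it through.** **Step 1: membership.** A subject lost during visits 1 to 12 has 0 Endexo treatments. The spop needs at least 1 and the apop at least 36, so the subject is in neither. Both that subject's events (numerator) and Optiflux treatments (denominator) leave the rate, whichever population is used.

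**Step 2: settling the 6.7/6.9 conflict does not cure this.** If 6.9 prevails, adverse events are summarised in the spop and Optiflux-period leavers are excluded. If 6.7 prevails, they are summarised in the apop and the exclusion is wider: SAP 2.1 permits four missed Endexo treatments, and 38 − 4 = 34 is below 36.

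**Step 3: direction.** The reported rate is too low if the leavers' own rate per treatment is above that of the retained subjects, and too high if it is below.

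**Step 4: size.** The plan has no figure to reproduce, because the documents state no event rate and no dropout rate. Inputs:

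- N enrolled: 15 to 24 (protocol synopsis).
- Optiflux treatments per retained subject: 12 (SAP 2.1), assuming none missed.
- Assumed: d = 1 to 3 leavers, each after 6 Optiflux treatments with a events each; retained rate r = 0.05 to 0.10 events per treatment.

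With rates pooled over treatments, the reported rate is r. The rate over all exposed subjects is [12(N − d)r + d·a] / [12(N − d) + 6d].

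| N | d | a | r | Rate over all exposed | Reported rate is |
|---|---|---|---|---|---|
| 15 | 2 | 2 | 0.05 | (156 × 0.05 + 4)/(156 + 12) = 11.8/168 = 0.070 | 29% too low |
| 15 | 3 | 0 | 0.05 | (144 × 0.05 + 0)/(144 + 18) = 7.2/162 = 0.044 | 12.5% too high |
| 24 | 1 | 1 | 0.10 | (276 × 0.10 + 1)/(276 + 6) = 28.6/282 = 0.101 | 1% too low |
| 15 | 3 | 2 | 0.05 | (144 × 0.05 + 6)/(144 + 18) = 13.2/162 = 0.081 | 39% too low |

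The last two rows are the extremes when every leaver has 1 or 2 events. A lower background widens the range. With r = 0.02 in the last row, the rate over all exposed is (2.88 + 6)/162 = 0.055, and the reported rate is 64% too low. With d = 0 the two rates coincide.

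**Step 5: the planned statistic.** SAP 5.1 averages within subject first. On that basis the first row becomes (13 × 0.05 + 2 × 2/6)/15 = 0.088, and the second becomes (12 × 0.05)/15 = 0.040, each against 0.050 reported. The direction is the same and the gap larger, because a leaver's short exposure carries the same weight as a full one.

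**The case against.** The case for leaving the plan alone has real force.

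- **The affected quantity is secondary.** The secondary objective in SAP 1.2 names adverse events with Endexo only. Optiflux is a cleared device that subjects must have been prescribed for at least 30 days before consent. Comparisons between periods are optional, and requiring exposure to both dialyzers is legitimate for a within-subject comparison. All of this stands, and it limits the importance of the point.
- **The events are not lost.** With 15 to 24 subjects the listings are easy to read, and the disposition table gives reasons for exit. A reader might infer that such events vanish from the report. The documents do not support that: what is missing is their place in the adverse event summaries.
- **The two periods may not be selected differently.** A reader might infer that the Endexo rate keeps its early leavers while the Optiflux rate does not. That is so only if SAP 6.9 prevails. Under 6.7, read with 6.9.1, both rates come from subjects with at least 36 Endexo treatments. The asymmetry cannot be asserted until those sections are reconciled.
- **The rule does not flatter the test device.** A reader might suspect that it favours Endexo, or that the Optiflux rate is always biased low. If exits are event-related, the low Optiflux rate makes Endexo look worse. If leavers had no events, the Optiflux rate is too high.
- **The sizes are assumed.** This is correct. The larger figures give each leaver 1 or 2 events in 6 treatments, and the 39% case leaves exactly 12 subjects, with no margin for the target of 12.

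None of this answers the narrower point: the plan reports an Optiflux event rate and excludes some subjects exposed to Optiflux because of what happened after that exposure began.

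**Conclusion.** The point holds as a defect in the population definitions. It follows from SAP 2.1 and 6.3 alone and needs no outside figure. An enrolled subject treated with Optiflux and lost before visit 13 contributes nothing to the Optiflux adverse event rate under either population.

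The size cannot be fixed from the documents. It is zero if nobody leaves in the Optiflux period. Under the stated assumptions (15 enrolled, 0.05 events per treatment among those retained, leavers exiting after 6 treatments, pooled rates), the reported 0.050 compares with 0.070 over all exposed when two leavers have two events each, and with 0.044 when three leavers have none.

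This is an accuracy fault in a control rate. The Endexo rate in the spop is unaffected, and nothing in the documents suggests that the rule was chosen to favour Endexo. The change should be made because it is cheap and because the plan itself foresees these exits.

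**What to change.** 1. Leave the spop as defined, for Endexo-period safety and for any within-subject comparison between periods.
2. Add an Optiflux safety set to the protocol and SAP 6.3: enrolled subjects with at least one study treatment on Optiflux. Use it for Optiflux-period adverse events.
3. Reconcile SAP 6.7 and 6.9.1 with 6.9, stating that adverse event rates use these two exposure-based sets and not the apop.

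The cost is one added definition in the protocol and SAP 6.3, a matching edit in SAP 6.7 and 6.9, and a different denominator for each period in the adverse event tables. No new data are needed, because events are already captured from consent. Endexo results computed in the spop do not change. If the sponsor had meant to use the apop for adverse events, step 3 would bring in Endexo-treated subjects with fewer than 36 treatments, so the sponsor should state which population was intended.

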## 6.4. Demographic and Other Baseline Characteristics

- Demographics, descriptive statistics will be presented for age, frequency and percent will be presented for sex, race and ethnicity.
- Dialysis history, frequency and percent of primary cause of ESRD will be presented.
- Medical history, all medical history recorded will be listed for each subject.

- Physical examinations, all recorded systems examined at the screening and follow-up will be listed.
- Vital signs, descriptive statistics will be presented for vitals recorded in the screening and follow-up.
- Initial prescriptions, the prescription will be listed for each subject.

## 6.5. Compliance

N/A

## 6.6. Analysis of Primary Endpoint

Descriptive statistics for ultrafiltration rate, TMP and ultrafiltration coefficient  $K_{uf}$  of the first study use (visit 13) of the dialyzer with Endexo will be presented under analysis population. A 95% confidence interval will be calculated if appropriate. These measurements observed/calculated for other timepoints (visits 24, 27 and 30) will be also presented with descriptive statistics.

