## 6.7. Analysis of Secondary Endpoints

All secondary endpoints will be analyzed under the analysis population.

For URR and spKt/V for the first study use of both dialyzers, descriptive statistics will be presented, and 95% confidence intervals will be calculated if appropriate. These measurements observed/calculated for other timepoints (every 3-4 weeks) will be also presented with descriptive statistics.

For serum albumin and  $\beta_2$ -microglobulin, the relative percent change  $\{((\text{pre-HD} - \text{post-HD})/\text{pre-HD}) \times 100\}$  will be calculated. Descriptive statistics will be presented for the pre-HD and post-HD laboratory values and the relative percent change. Percent changes will also be calculated using corrected  $\beta_2$ -microglobulin concentrations based on the equation published by Bergström and Wehle. The 95% confidence interval will be derived if appropriate.

Adverse events will be coded for system organ class (SOC) and preferred term using Medical Dictionary for Regulatory Activities (MedDRA), Version 20.0. Adverse events and device-related events per treatment will be calculated. The 95% confidence intervals will be derived if appropriate.

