## 6.8. Analysis of Exploratory Assessments

All exploratory assessments will be analyzed under analysis population.

For the measurements of complement activation, the relative percent change  $\{((30 \text{ minutes after the recorded start of HD} - \text{pre-HD})/\text{pre-dialysis}) \times 100\}$  will be calculated. Descriptive statistics

will be presented for the “pre-dialysis” and “30 minutes after the recorded start of HD” laboratory values and the relative percent change. The 95% confidence intervals will be calculated if appropriate.

For thrombus formation:

- the number of subjects and percentages, and the number of dialysis treatments in each period for each grade category will be presented, and,
- the proportion of treatments with full dialyzer clotting will be calculated for each subject in each period. Descriptive statistics of the proportions will be presented. A 95% confidence interval of the proportions will be calculated if appropriate.

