### **6.9.2 Clinical Laboratory Evaluation**

Descriptive statistics will be presented for each test and timepoint required by the protocol. Changes between test results from pre-dialysis and post dialysis will also be presented for blood samples collected pre- and post-dialysis.

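### SAP 6.6–6.8 summarise first-use endpoints, including the primary visit-13 Kuf, only in subjects who later reach 36 Endexo treatments, so three or four permitted misses, or withdrawal before the 36th treatment, remove a valid first-use value

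*SAP*

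**What the plan says.** SAP 6.6 states that descriptive statistics for ultrafiltration rate, TMP and Kuf "of the first study use (visit 13) of the dialyzer with Endexo will be presented under analysis population", with a 95% CI where appropriate. For the later Kuf readings it adds: "These measurements observed/calculated for other timepoints (visits 24, 27 and 30) will be also presented with descriptive statistics".

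SAP 6.7 says "All secondary endpoints will be analyzed under the analysis population". These include URR, spKt/V, albumin and beta-2-microglobulin at the first study use of each dialyzer (visit 1 for Optiflux, visit 13 for Endexo). SAP 6.8 says "All exploratory assessments will be analyzed under analysis population", which takes in first-use complement.

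SAP 6.3 defines the analysis population as safety-population subjects who "have a minimum of 36 HD treatments with the dialyzer with Endexo". The safety population needs only one Endexo treatment.

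On attendance, SAP 2.1 schedules 38 Endexo treatments (visits 13–50) and says: "The visit 13 cannot be missed. A maximum of four missed treatments are permitted within Visits 14-50".

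Two other passages bear on the point. SAP 6.9 says "All safety measurements will be analyzed under safety population", and under it SAP 6.9.2 says "Descriptive statistics will be presented for each test and timepoint required by the protocol", together with pre- to post-dialysis changes. SAP 5.1 lists all data.

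The Protocol Synopsis (Statistical Methods) defines the same two populations but does not assign the primary endpoint to either.

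**The concern.** A first-use measurement is complete at visit 13. Whether the subject enters its summary is settled about 12 weeks later, by a treatment count. Thirty-six treatments are not needed to obtain or interpret a Kuf reading taken 15 minutes into the first session.

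The SAP's own rules make this concrete. Visit 13 is mandatory, so the value should exist for every subject who enters the Endexo period. A subject can then stay within the attendance rule and still be left out of the primary summary because of sessions missed after the measurement.

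At stake are precision in a study of 15–24 enrolled subjects and the meaning of the summary, which describes first use among those who later attended rather than among all who used the device. The descriptive mean and its CI are the whole primary result, so it matters who is in them.

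**Working it through.** **Inputs from the documents.** Endexo treatments scheduled: 38 (SAP 2.1). Later visits that may be missed: up to 4 of 37 (SAP 2.1). Threshold: 36 (SAP 6.3). Enrolment 15–24, to obtain at least 12 subjects with 36 treatments (Protocol Synopsis; SAP 2.5). The sample size comes from a guidance minimum, so there is no power or precision formula to reproduce.

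**Step 1: count.** Visits 13 to 50 give 50 − 13 + 1 = 38 treatments. Assume that missed sessions are not made up.

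| Misses in visits 14–50 | Endexo treatments | Within attendance rule | In analysis population |
|---|---|---|---|
| 0 | 38 | yes | yes |
| 1 | 37 | yes | yes |
| 2 | 36 | yes | yes |
| 3 | 35 | yes | no |
| 4 | 34 | yes | no |

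Withdrawal before the 36th Endexo treatment also excludes. Withdrawal after it does not.

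**Step 2: what is summarised elsewhere.** SAP 6.9.2 would show measured laboratory values and their pre/post changes in the safety population. Kuf is not a laboratory test; it is UF rate divided by TMP (SAP 4.1). URR and spKt/V are derived quantities. No safety-population summary is planned for Kuf, URR, spKt/V or the formal endpoint CIs.

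**Step 3: how many subjects (assumed miss rates).** The documents give no miss rate. With independent misses at rate m per session, and no withdrawals:

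P(3 or 4 misses) = C(37,3)·m³·(1−m)³⁴ + C(37,4)·m⁴·(1−m)³³

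| m | P(3 or 4) | Expected of 15 | Expected of 24 |
|---|---|---|---|
| 1% | 0.0060 | 0.1 | 0.1 |
| 2% | 0.0367 | 0.6 | 0.9 |
| 3% | 0.0941 | 1.4 | 2.3 |
| 5% | 0.2458 | 3.7 | 5.9 |

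Misses probably cluster within subjects. Under a beta-binomial with correlation 0.05 to 0.10, the expected number of 15 is 0.4–0.5 at 1% and 1.8–2.5 at 5%, inside the same range. Loss through withdrawal is not quantified.

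**Step 4: precision.** The 95% CI half-width in SD units is t(0.975, n−1)/√n.

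- n = 15: 2.145/√15 = 0.554
- n = 12: 2.201/√12 = 0.635
- Ratio: 0.635/0.554 = 1.147, about 15% wider

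This is the plan's low-end case (15 enrolled, 12 analysed). It is an upper bound for that case, because some of the three losses may come before visit 13, and those subjects have no Endexo first-use value to recover.

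**The case against.** The strongest defence is that the choice is deliberate and prespecified. The guidance, as the documents cite it, asks for data on at least 12 subjects with 36 treatments each. The protocol defines just these two populations immediately before the endpoint analyses, so using the analysis population for endpoints is a natural reading of it. One fixed set also keeps the same subjects across Kuf at visits 13, 24, 27 and 30. This stands as a reason to keep the set for the guidance count and for that comparison. It gives no reason why a visit-13 value should depend on the count: the cited recommendation concerns how much data to collect, and the documents do not say that first-use values must come only from those subjects.

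It can also be said that little is lost, since all values are listed and laboratory results appear in the safety tables. That holds for albumin, beta-2-microglobulin, complement and BUN where the protocol requires them. It does not cover the quantities named in step 2, and a listing is not a summary.

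Make-up sessions, if allowed, would reduce exclusions through misses. Withdrawal before the 36th treatment would still exclude.

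A reader might infer that any later miss or any withdrawal removes a subject. The count does not support that: one or two misses, or withdrawal after the 36th treatment, leave the subject in. A reader might also infer that the four-miss limit contradicts the 36-treatment threshold. It does not: one governs permitted attendance and the other membership of an analysis set, and the two can coexist.

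**Conclusion.** The point holds and is minor. Under SAP 6.3 with 6.6–6.8, a subject with a mandatory, valid first-use value is left out of the primary and other first-use summaries after three or four permitted misses, or after withdrawal before the 36th Endexo treatment. The part about misses assumes that there are no make-up sessions.

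The size depends on a miss rate that the documents do not give: 0.1 to 3.7 of 15 subjects at an assumed 1–5% per session with independent misses. At the low end of the enrolment range the CI is up to 15% wider.

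It would be tempting to conclude that the primary result is biased. The documents do not support this: nothing in them links first-use Kuf to later attendance. The study is descriptive, so no power or decision limit is affected. What is shown is a loss of precision and a summary conditioned on later attendance.

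**What to change.** In SAP 6.6–6.8, replace the population wording for first-use endpoints, and limit the blanket sentences on secondary endpoints and exploratory assessments to match. Adding text without changing those sentences would leave a contradiction. Suggested wording:

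*Endexo first-use endpoints (visit 13) are analysed in all safety-population subjects with a valid measurement at that visit. Optiflux first-use endpoints (visit 1) are analysed in all enrolled subjects with a valid visit-1 measurement. Between-dialyzer comparisons use subjects with both values.*

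The Optiflux sentence refers to enrolled subjects because the safety population requires an Endexo treatment. Using it for visit 1 would again condition a first-use value on later attendance.

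Keep the 36-treatment population for three purposes: the guidance count (12 subjects × 36 treatments), a supporting summary of the same first-use endpoints, and Kuf at visits 13, 24, 27 and 30 in the same subjects. Neither the four-miss limit nor the threshold of 36 changes.

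The cost is a few SAP sentences and one supporting table per first-use endpoint, with no extra subjects, visits or samples. The downside is that n differs between tables, so each table should state its n.
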